#### 8.1.1 Safety/Tolerability

The primary safety endpoint is defined as the proportion of subjects free of TENS - related serious adverse events and/or adverse device effects through the therapy phase (safety success rate). The AE and/or ADE rates will be summarized utilizing descriptive statistics and compared utilizing parametric and non-parametric methods as deemed appropriate. The null and alternative hypotheses are:

```
H_0: π_T ≤ π_C
H_1: π_T > π_{C}
```

Where  $\pi_T$  and  $\pi_C$  are the probabilities of adverse events and/or adverse device effects in treatment versus historical control respectively.

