#### 6. STUDY ENDPOINTS

#### 6.1 PRIMARY ENDPOINTS

#### **6.1.1 Primary Safety/ Tolerability Endpoints:**

- Safety/Tolerability will be assessed by the non-inferiority of incidence of serious adverse events (SAEs), unanticipated SAES (USAEs), device-related SAEs (DSAEs) and Unanticipated Device Related SAEs (UDAEs) that are associated with the TENS therapy throughout the therapy/treatment period versus historical control.
- Safety variables will be tabulated and presented for all subjects including enrolled, but discontinued, subjects. Number of subjects undergoing TENS and any reasons for discontinuation of study treatment will be tabulated.

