#### 9.12.1 General information on Stimulation:

The TENS unit utilizes low intensity electrical stimulation to activate nerve endings under the skin. While response to TENS varies typically subjects report a mild tingling or burning sensation during and immediately after stimulation session. In addition, mild numbness, termed paresthesia, may be experienced.

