#### 9.12.2 Starting the Therapy Phase

During the Therapy Phase, the subject's TENS is programmed to the following settings:

Parameter	Suggested Initial Setting
Frequency	30 Hz
Pulse-Width	200µs
Amplitude	Up to 30 mA sustained (up to 40mA peak)

It is also important that the subject complete the diary during this period. If subject does not feel sensation, subject is to notify PI or Coordinator because it may indicate improper device function. The TENS unit will be replaced if dropped or becomes defective and non-functioning. It is recommended that subjects confirm response to stimulation during the office visits.

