#### 10.1.2 Risks associated with appetite loss

While appetite loss is beneficial to weight loss, severe appetite suppression may place the subject at risk for hypoglycemia and dehydration which may entail risks to alertness and other conditions. Prolonged appetite suppression can cause alterations in mood and mental acuity and impact activities of daily living (ADL).

Adverse Events: The adverse events listed below are anticipated to occur at low frequency, and the subject needs to be aware that they may occur.

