#### From TENS:

Paresthesia

Burning sensation

Pair

Skin irritation (urticaria) at or near the electrode application site

Redness at site of stimulation

Mild swelling at site of electrode stimulation

Nausea

GI discomfort

Dyspepsia

Heartburn

Cramping

Gastroparesis

From appetite loss:

Mild hypoglycemia

Dehydration

Alterations in mood Mild trouble sleeping Alterations in mental acuity Anorexia

From potential use of anti-nausea medication (PI Discretion):

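### Sections 6.1.1 and 8.1.1 define the primary safety endpoint differently, and under 8.1.1 an expected, harmless stimulation sensation can be scored as a safety failure

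*Combined protocol and SAP*

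**What the plan says.** **Two definitions of primary safety.** Section 6.1.1 assesses safety by "non-inferiority of incidence of serious adverse events (SAEs), unanticipated SAES (USAEs), device-related SAEs (DSAEs" and unanticipated device-related SAEs, against historical control. The Study Endpoints part of the Protocol Summary uses the same four classes and identifies the historical control as other TENS systems. Section 8.1.1 instead defines the endpoint as "the proportion of subjects free of TENS - related serious adverse events and/or adverse device effects through the therapy phase". It then takes the hypotheses to concern the "probabilities of adverse events and/or adverse device effects in treatment versus historical control respectively", where the word serious does not appear.

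**How sensation is described.** Section 9.12.1 says that "typically subjects report a mild tingling or burning sensation during and immediately after stimulation session", that mild numbness (which it calls paresthesia) may occur, and that response varies. Section 9.12.2 says: "If subject does not feel sensation, subject is to notify PI or Coordinator because it may indicate improper device function". Section 10.1.1 names numbness, tingling and burning among the device risks, yet also asks subjects to make contact if the therapeutic sensation is missing. The list of adverse events from TENS that follows Section 10.1.2 includes paresthesia and "Burning sensation", with no severity or duration qualifier. That list is introduced by "The adverse events listed below are anticipated to occur at low frequency".

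**Event definitions.** Section 11 requires an adverse event to be undesirable and makes no exemption for expected sensation. Section 11.2 defines only the unanticipated adverse device effect. Section 9 and Appendix 6 have ADEs assessed at visits in the treatment group only.

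**The concern.** A primary endpoint must say which subjects are failures. Here the endpoint section and the analysis section give different answers, and nothing says which prevails. The broader version rests on a term that has no definition, and the sensations it may capture are ones the protocol expects during normal operation.

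The endpoint in 8.1.1 is an any-event measure over the whole therapy phase. At the scheduled three sessions a day for 12 weeks there are 3 × 7 × 12 = 252 sessions, and a single recorded sensation is enough to end success. If some sites record tingling or burning as an ADE and others regard it as the therapy working, the rate partly reflects recording habit. The comparison with historical control has the same weakness, because the documents do not say how sensation was coded there.

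**Working it through.** The documents give no safety figure to reproduce: no historical rate, non-inferiority margin or expected success rate. The check is therefore a comparison of texts, followed by an illustration of how far the result can move.

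**Step 1: the same subject under each definition.** Take a treated subject who has mild burning during sessions and no other event.

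| Question | Section 6.1.1 and Summary | Section 8.1.1 |
|---|---|---|
| Events that count | Four classes of serious event | TENS-related SAEs and/or ADEs; hypotheses on AEs and/or ADEs |
| Seriousness limit | Yes | None in the definition of the probabilities |
| Sensation not recorded as an ADE | Not a failure | Not a failure |
| Sensation recorded as an ADE | Not a failure | Failure, if serious is not read as also governing ADEs |

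**Step 2: does any text settle the last row?** Section 9.12.1 calls mild tingling or burning typical. Burning is on the adverse event list, and tingling and numbness are among the risks in 10.1.1. Section 11 leaves it to the investigator whether the occurrence is undesirable. ADE is undefined. No section states whether an expected sensation is recorded.

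**Step 3: range of the 8.1.1 success rate.** Let q be the share of treated subjects whose sensation is recorded as an ADE, and s the share with a TENS-related SAE. Both are assumptions. Treating them as independent, success = (1 − s)(1 − q). With n = 75 treated (Section 8.2) and s = 0:

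| q | Success under 8.1.1 | Subjects of 75 | Success on serious classes only |
|---|---|---|---|
| 5% | 95% | 71.3 | 100% |
| 10% | 90% | 67.5 | 100% |
| 25% | 75% | 56.3 | 100% |
| 50% | 50% | 37.5 | 100% |
| 75% | 25% | 18.8 | 100% |
| 90% | 10% | 7.5 | 100% |
| 100% | 0% | 0 | 100% |

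With s = 2% and q = 90%, success is 0.98 × 0.10 = 9.8%. With s = 2% and q = 0 it is 98%. The recording choice can move the result far more than a small rate of serious events does.

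**Step 4: what a serious-only endpoint can show.** With 0 events in 75 subjects, the one-sided 95% upper bound is 1 − 0.05^(1/75) = 3.9%.

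**The case against.** The strongest reply is that no section says a subject who feels the stimulation fails. That result needs three conditions together: serious in 8.1.1 does not govern ADEs; the investigator judges the sensation undesirable and records it; and 8.1.1 prevails over 6.1.1 and the Summary. The phrase in 8.1.1 is grammatically open. Section 10.1.1 calls the sensation therapeutic, and the concept statement in Appendix 9 describes tingling as how treatment feels, which suggests that the sponsor sees it as device function. The clear overlap between the typical sensations and the adverse event list is burning alone: tingling appears only among the risks, and numbness is only possible. The stated low frequency of listed events points to the lower end of q.

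Most of this stands, and it rules out three stronger readings that a reader might infer.

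- *Every correctly treated subject fails.* Failure is possible, not stated, and Section 9.12.1 says that response varies.
- *The success rate falls as the device works better.* Section 9.12.2 says only that absent sensation may signal a fault. It does not link sensation to weight loss.
- *The rate says nothing about harm.* If sensation were coded alike in the historical control it would enter both rates. What is missing is a common coding rule.

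The reply does not remove the contradiction. The probabilities in 8.1.1 carry no seriousness limit, and both the general text of Section 8 and the objectives in Section 4 also speak of adverse events and ADEs without one. The broad reading is at least as well supported as the narrow one.

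**Conclusion.** The concern holds as an internal contradiction. The primary safety endpoint is limited to serious classes in 6.1.1 and the Summary, but it reaches ADEs in 8.1.1. With ADE undefined and expected sensation overlapping with listed risks and adverse events, the 8.1.1 rate can lie anywhere from 100% to 0% without any harm, while under 6.1.1 the same subjects are not failures.

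That range is not a forecast. The documents give no recording rate, and the word typically in 9.12.1 describes how often sensation is felt, not how often it is recorded as an ADE. The figures also assume 75 treated subjects and, in the main table, no serious events. The low frequency stated in 10.1.2 and the typical sensation in 9.12.1 conflict to the extent that ordinary mild burning is the event listed; the documents do not say whether it is. The direction of the printed hypotheses in 8.1.1 is a separate matter.

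**What to change.** Put the endpoint and the definition of the probabilities in 8.1.1 on the serious event classes of 6.1.1, and tabulate non-serious ADEs by type as tolerability. This is protocol and case report form wording. The cost is that non-serious device effects leave the primary safety rate. Few serious events are likely for a study described as non-significant risk, so the endpoint will have limited resolution (the 3.9% bound at 0 of 75).

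If the sponsor intends ADEs to stay in the primary endpoint, which the objectives in Section 4 could support, then amend 6.1.1 and the Summary to match. Define ADE in Section 11, state whether expected stimulation sensation counts, and apply the same coding to the historical control. The cost is that historical sources without compatible coding could not be used directly.

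In either case, reconcile the frequency statement in 10.1.2 with the description in 9.12.1. Any threshold at which a sensation becomes an ADE is for the sponsor to set, and it should be fixed before data are reviewed.

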## Study Endpoints

#### Primary Safety/Tolerability Endpoint:

Safety/Tolerability will be assessed by the non-inferiority of incidence of serious adverse events (SAEs), unanticipated SAEs(USAEs), device-related SAEs (DSAEs) and Unanticipated Device Related SAEs (UDAEs) that are associated with the TENS therapy throughout the stimulation and the follow-up period versus historical control (compared with other TENS systems).

Safety variables will be tabulated and presented for all subjects including enrolled, but discontinued, subjects. Number of subjects undergoing active stimulation and any reasons for discontinuation of study treatment will be tabulated.

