#### 4. STUDY OBJECTIVES

The objectives of this study are to demonstrate safety and effectiveness of a wearable patch TENS system (Appendix 2) in driving weight loss when coupled with an integrated weight loss reduction strategy. The study is designed to demonstrate that TENS stimulation sufficient to drive weight loss is safe and tolerable when compared to standard of care, and that adverse events/adverse device effects are similar to other TENS device use cases.

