#### 8.1.2 Appetite Suppression

The null and alternative hypotheses are:

$$H_0$$
:  $π_T ≤ π_C$ 
 $H_1$ :  $π_T > π_C$ 

Where  $\pi_T$  and  $\pi_C$  are the probabilities of appetite suppression in treatment versus control respectively. Pearson correlation will be utilized to correlate appetite score (as measured with TFEQ-18V2; ) with stimulation dose. Estimates of 95% confidence intervals will also be computed for the difference between varying levels of stimulation. Wilcoxon signed rank tests and/or Kruskal Wallis statistics will be utilized to make comparisons between groups as required. Estimates and 95% confidence intervals will also be computed for the difference in appetite levels between Baseline and Therapy Periods.

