#### 8.1.3 Weight Loss

The null and alternative hypotheses are:

$$H_0$$
:  $π_T ≤ π_C$ 
 $H_1$ :  $π_T > π_C$ 

Where  $\pi_T$  and  $\pi_C$  are the probabilities of weight loss (% TBWL, %EBWL) in treatment versus control respectively. Estimates of the proportion of weight loss in pounds, % total body weight loss (%TBWL) Excess Body Weight Loss (%EBWL) or BMI will be compared with a tested Fishers Exact Test. Estimates and 95% confidence intervals will also be computed for the difference in rate of weight loss between varying stimulation levels.

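### The primary safety hypotheses in section 8.1.1 are not a non-inferiority test: as written they can only show harm, on the event-free scale they demand superiority, and no margin is given

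*Combined protocol and SAP*

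**What the plan says.** The aim is stated three times. Section 6.1.1 says "Safety/Tolerability will be assessed by the non-inferiority of incidence of serious adverse events" and related categories, against a historical control; the Protocol Summary says the same and identifies that control as other TENS systems. Section 4 makes it an objective that "adverse events/adverse device effects are similar to other TENS device use cases".

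Section 8.1.1 then turns this into a test in two steps that use opposite scales:

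- The endpoint: "The primary safety endpoint is defined as the proportion of subjects free of TENS - related serious adverse events and/or adverse device effects", called the safety success rate. Higher is better.
- The hypotheses: H0: `π_T ≤ π_C`, H1: `π_T > π_C`, where the two π's "are the probabilities of adverse events and/or adverse device effects in treatment versus historical control respectively". Higher is worse.

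The same H0/H1 pair stands in section 8.1.2, where the π's "are the probabilities of appetite suppression in treatment versus control respectively", and in section 8.1.3, where they "are the probabilities of weight loss (% TBWL, %EBWL) in treatment versus control respectively". In both of those, a larger π is the favourable result.

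Section 8.1.1 leaves the choice of parametric or non-parametric method open. Section 8 adds propensity-score and sensitivity analyses against the historical control, and confidence intervals for proportions and their differences, but no decision rule.

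**The concern.** A non-inferiority test places unacceptable excess risk in the null hypothesis and needs a margin that says how much excess is unacceptable. The lines in 8.1.1 do neither. The direction suits the benefit outcomes of 8.1.2 and 8.1.3, so carrying those lines over to safety is a likely cause.

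The event being counted also moves: serious-event categories in 6.1.1, TENS-related serious events and/or device effects in the 8.1.1 endpoint, and adverse events and/or device effects without a seriousness qualifier in the definition of π.

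This is a primary endpoint of a study that the Protocol Summary calls pivotal. If the text is followed, the safety verdict depends on which sentence of 8.1.1 the analyst takes up. The study is also open label, so a margin or event definition chosen after data have accumulated would carry little weight.

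**Working it through.** **Step 1: direction (no assumptions needed).**

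| Reading of π in 8.1.1 | What H1 `π_T > π_C` claims | What follows |
|---|---|---|
| Event probability (as defined) | More events than historical control | Rejection shows harm; non-rejection is not evidence of non-inferiority |
| Event-free probability (the endpoint's scale) | Strictly fewer subjects with events than historical control | Superiority with zero margin; an equally safe device passes with probability at most alpha |
| Non-inferiority, event scale (6.1.1) | Would be `π_T − π_C < δ` | Cannot be obtained from either reading, because there is no δ |

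**Step 2: missing inputs.** The documents give no δ, no historical TENS event rate and no alpha for this test. The report of no complications in section 1.3 comes from a percutaneous-stimulation study, not from other TENS systems. The sample size in section 8.2 rests on weight loss only. There is therefore no safety figure in the plan to reproduce.

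**Step 3: illustration.** From the documents: 75 treated (section 8.2), with all enrolled subjects analysed for safety (section 8.4). Assumed: historical rate p0 from 1% to 20%, treated as known; one-sided alpha of 5%, or 2.5% to match the two-sided 95% intervals in section 8; full follow-up of all 75. X is the number of treated subjects with an event, X ~ Binomial(75, p). This does not model the planned propensity-score comparison.

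*Event-free reading.* Zero events reject H0 only if (1 − p0)^75 ≤ alpha, that is p0 ≥ 1 − alpha^(1/75):

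- 1 − 0.05^(1/75) = 3.9%
- 1 − 0.025^(1/75) = 4.8%

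Above that, the device passes if X ≤ c, with c the largest value for which P(X ≤ c given p0) ≤ alpha. The cut-offs are the same at both alphas.

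| p0 | c | P(pass), equal rate | P(pass), half the rate |
|---|---|---|---|
| 5% | 0 | 0.95^75 = 2.1% | 0.975^75 = 15% |
| 10% | 2 | 1.6% | 27% |
| 20% | 8 | 2.4% | 67% |

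*Literal reading.* H0 is rejected if X ≥ k, with k the smallest value for which P(X ≥ k given p0) ≤ alpha. If non-rejection were taken to mean safe (a rule the plan does not state), a device with twice the historical rate would pass as follows:

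| p0 | k, alpha 5% | Passes at 2·p0 | k, alpha 2.5% | Passes at 2·p0 |
|---|---|---|---|---|
| 1% | 3 | 81% | 4 | 94% |
| 2% | 5 | 82% | 5 | 82% |
| 5% | 8 | 52% | 9 | 67% |
| 10% | 13 | 24% | 14 | 34% |
| 20% | 22 | 2% | 23 | 4% |

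For frequent events this second problem is small.

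**Step 4: what a proper test could support.** To pass an equally safe device at least 80% of the time, find the smallest allowed count x with P(X ≤ x given p0) ≥ 0.80, take the exact upper confidence bound U at x events, and require δ > U − p0.

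| Treated | p0 | x (pass probability) | U, one-sided 5% / 2.5% | δ must exceed (points) |
|---|---|---|---|---|
| 75 | 1% | 1 (0.827) | 6.17% / 7.21% | 5.2 / 6.2 |
| 75 | 10% | 10 (0.874) | 21.57% / 23.16% | 11.6 / 13.2 |
| 150 | 1% | 2 (0.809) | 4.14% / 4.73% | 3.1 / 3.7 |

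The 150 row assumes the maximum enrolment of 300, split equally.

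**The case against.** The best reply is that the intent is plain. The Protocol Summary and sections 4 and 6.1.1 all say no worse than, or similar to, other TENS use, and no sensible analyst would report success after finding more events. On this view the inverted sign is a copying slip. It may well be, but correcting the sign does not rescue the plan: it turns the test into superiority, still without a margin, a rate or an alpha. Nor do the intervals promised in section 8 fill the gap, since no bound is named that would count as success.

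Several narrower points stand as limits on the illustration:

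- Section 8.1.1 never defines π as event-free; that reading comes from the endpoint sentence that precedes it.
- The literal-reading pass rates depend on a decision rule that the plan does not contain.
- Full follow-up of 75 is optimistic. Section 8.2 assumes 30% drop-out, and 75 × 0.7 = 52.5. With 52 followed throughout, zero events bound the rate at 1 − 0.05^(1/52) = 5.6% or 1 − 0.025^(1/52) = 6.8%, rather than 3.9% or 4.8%.
- In the endpoint sentence, the word serious may be meant to cover device effects too, which would bring it nearer to 6.1.1. The unqualified wording in the definition of π remains different.
- Section 9.12.1 describes mild tingling or burning as typical, while the adverse event list in section 10.1 includes paresthesia and burning and introduces its entries with "The adverse events listed below are anticipated to occur at low frequency". An expected mild sensation is not automatically an adverse event under section 11, so these need not conflict. They show only that the choice of event could change the rate a great deal.

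None of these points supplies the missing test.

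**Conclusion.** The concern holds and must be fixed. As defined, H1 in 8.1.1 is harm; on the endpoint's own scale it is superiority; neither is the promised non-inferiority, and the inputs for a non-inferiority test are absent. This follows from the text and does not depend on any assumed rate.

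The size is illustrative only, under the assumptions in the working. On the event-free reading, a device exactly as safe as historical TENS would fail about 98% of the time at historical rates of 5% to 20%, and could never pass at 1% or 2%. On the literal reading, treating non-rejection as reassurance would let a doubled rate through in 24% to 94% of trials at historical rates of 1% to 10%. Sampling error in the historical data is ignored; allowing for it would widen the bounds.

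**What to change.** Rewrite 8.1.1 on one scale. With π as event probability:

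- H0: `π_T − π_C ≥ δ`; H1: `π_T − π_C < δ`.
- Conclude non-inferiority if the upper confidence bound for the difference lies below δ.
- Fix δ, π_C with its source, and alpha before the data are seen.
- Use one event definition in the Protocol Summary, 6.1.1 and 8.1.1. The sponsor should decide whether adverse device effects belong in it: the 8.1.1 endpoint includes them, and section 4 makes their similarity to other TENS use an objective.
- State whether the propensity-score comparison in section 8 is the primary safety analysis, and how incomplete follow-up is handled.

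The cost is protocol and SAP wording plus the work of sourcing π_C and justifying δ; no visits or data collection are added. The price in the claim is that it is limited to what the sample can exclude. With 75 treated and an assumed 1% historical rate, a δ just above 5.2 points tolerates a rate of about 1 + 5.2 = 6.2%, some six times historical. If no margin that the sponsor can defend is reachable at this size, the non-inferiority claim should be dropped and safety reported descriptively with confidence intervals.
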